Twenty (N=20) individuals at University of British Columbia with physician diagnosed T1D (N=10) or T2D (N=10) (HbA1c 6.5-8.5%), between the ages of 18-75 years, with a BMI between 25-40 kg/m² will be recruited through online social media and newspaper advertising.

Inclusion criteria will be: i) physician-diagnosed T1D or T2D of ≥1 year; ii) current HbA1c of 6.5-8.5%; iii) BMI: 25-40 kg/m2; iv) blood pressure of <160/99 mm Hg assessed according to guidelines; v) non-smoking; vi) not on hormone

replacement therapy, corticosteroids, or anti-inflammatory medications; and vii) 18–75 years old. **Exclusion criteria will include** i) Are taking more than 2 glucose lowering medications; ii) Are ongoing medical treatment for diseases such as cancer, auto-immune or inflammatory disease, liver or kidney disorders; iii) Have allergy, intolerance or aversion to cocoa, stevia, erythritol, inulin, or any other dietary restrictions (e.g., vegan) that will prevent them from following the standardized study diets; iv) Are unable to follow remote guidance by internet or smartphone; v) Are unable to follow the controlled diet instructions; vi) Are unable to read or communicate in English.

Based on our previous studies ~55% of males and ~70% of females with T1D or T2D who volunteer will meet these eligibility criteria so we anticipate no recruitment issues. We will allow statins and anti-hypertensive medications if on a stable dose for 3 months because the majority of T2D patients are on at least one of these medications; excluding them would leave a small pool for recruitment and limit the generalizability of our findings. Interested participants will provide their e-mail to establish direct and individual communication with research team.

A double-blinded crossover pilot trial is proposed. Eligible participants will complete 2 experimental trials separated by approximately 2-7 days, consuming no-sugar dark chocolate from Ross Chocolates and a conventional dark chocolate bar.

Due to COVID-19 breakout, this study is proposed to be done remotely since participants belong to risk group and will probably maintain in quarantine for unpredictable time. Information and guidance for the trial will be done by email, telephone calls and Zoom meeting. RedCap-UBC will be used to manage information and deliver questionnaires. Participants will be recruited after completing an online Eligibility questionnaire.

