Participants will receive in their homes a box containing a OneTouch Verio IQ® kit Blood glucose monitoring system (OneTouch Verio IQ® meter, lancing device, sterile lancets, carrying case), glucose strips, alcohol swabs, 1 bar of Ross dark chocolate (34g each) and 1 bar of a conventional dark chocolate (34g each) and instructions on how to proceed during each trial. Chocolate bars will be identical and wrapped equally and labeled as A and B, by Ross Chocolates (prepared in the same mold and packaged identically) who are not involved in any other aspects of the study, allowing for blinding of research team and participants. Participants will complete two experimental trials: 1) consumption of 1 bar (34g) of Ross dark chocolate 2) consumption of 1 bar (34g) of conventional dark chocolate. The order of the bars will be randomized so there will be an equal chance of getting bar A or bar B first (similar to drawing a name out of a hat or flipping a coin). Participants will be advised to perform both trials on the exact same time of day, in the morning after an overnight fast, refraining from diabetic medications. They will be asked to register glucose levels before and after eating the chocolates. A OneTouch Verio

IQ® meter will be used to measure blood glucose. Time points will be as follows: before consumption, 15 min after, 30min after, 45min after, 60min after, 90min after, 120min after. Values will be registered on a Glucose Form and stored on the meter and sent to research team by email. Participants will then be asked to Complete Taste Test Questionnaire sent by RedCap link through e-mail.

Study Timeline:

Baseline Contact

On the initial contact, by a FIRST email, participants will be informed of the study and asked to complete a Health Screening Questionnaire and sign electronically an Informed Consent. After confirmation of eligibility and given consent, participants will receive a SECOND email with information on the study kit and asked to inform Research team when kit arrives. The kit will contain:

- Study Welcoming, Instructions and Responsibilities
- Glucose levels form
- OneTouch Verio IQ® kit Blood glucose monitoring system (OneTouch Verio IQ® meter, lancing device, sterile lancets, carrying case)
- Glucose strips
- Alcohol swabs
- 1 bar of dark chocolate A (34g each)
- 1 bar of dark chocolate B (34g each)

Once participants confirm study kit was received, they will get a THIRD email suggesting to start the protocol.

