Participants will choose 2 different days, one for Day 1 and one for Day 2 (2-7 days apart from each other) and perform the following protocol:

Day 1

- ✓ Measure glucose levels before chocolate consumption and write down value on Glucose levels form
- ✓ Consume 1 bar of dark chocolate (A or B) according to instructions from Research team after randomization

- ✓ Measure glucose levels after consumption (15 min, 30 min, 45 min, 60 min, 90 min, 120 min) and write down values on Glucose levels form
- ✓ Complete Taste Test Questionnaire sent to participant's e-mail

Day 2

- ✓ Measure glucose levels before chocolate consumption and write down value on Glucose levels form
- ✓ Consume 1 bar of dark chocolate (A or B) according to instructions from Research team after randomization
- ✓ Measure glucose levels after consumption (15 min, 30 min, 45 min, 60 min, 90 min, 120 min) and write down values on Glucose levels form
- ✓ Complete Taste Test Questionnaire sent to participant's e-mail
- ✓ Send photo of Glucose levels form by email

A Zoom meeting will be scheduled to guide participants with procedures in study if necessary.

Statistical Analysis

Changes in blood glucose across time between conditions will be analyzed with a linear mixed effects model including time, condition, and their interaction as fixed effects and participant ID and baseline glucose values as random effects. Area under the curve and incremental AUC will be calculated and analyzed by paired t-test.

Sample size

Sample size calculation for a within-between interaction with alpha of 0.05, power of 80%, and an expected moderate effect size (f=0.25) reveals a sample size of 12 is needed to detect a significant difference. To preserve power and enable potential sub-analyses of type 1 vs. type 2 diabetes we will aim to recruit 20 participants for this preliminary study.

Significance

The results of this study will help determine whether by consuming a dark chocolate bar sweetened with stevia, erythritol, and inulin will cause a blood glucose spike in people with diabetes (T1D and T2D). This information will provide high quality scientific evidence which will allow individuals with diabetes more food choices, helping them manage diabetes better.

OUTCOMES MEASUREMENTS AND METHODS

The primary outcome measure is plasma glucose levels following consumption of the dark chocolate bars. The taste of the chocolates will also be evaluated.

Glucose Monitoring

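### The mixed model's random effects are constant within a visit, so unless a residual structure is added, individual curve shape and serial correlation stay in the error and the condition-by-time test need not hold 5%

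*Combined protocol and SAP*

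**What the plan says.** The Statistical Analysis section gives one model for the glucose curves, a linear mixed model "including time, condition, and their interaction as fixed effects and participant ID and baseline glucose values as random effects". It does not mention a participant-by-time term, a residual covariance structure, a sphericity correction or a degrees-of-freedom method, and it does not say whether time is categorical or linear. Paired t-tests are planned alongside it for total and incremental AUC.

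The Research Method section describes the data. "A double-blinded crossover pilot trial is proposed", so every participant eats both bars. Glucose is read "before consumption, 15 min after, 30min after, 45min after, 60min after, 90min after, 120min after", that is, seven times per visit and 14 times per participant. The target is 10 people with T1D and 10 with T2D, fasted and off their diabetes medication. The Sample size section assumes a "within-between interaction with alpha of 0.05", 80% power and f = 0.25, and arrives at 12. It states no correlation and no sphericity assumption.

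**The concern.** A participant intercept moves that person's whole curve up or down. Baseline glucose takes one value per visit, so as a random effect, whether as a grouping factor or as a slope, it can only add a further constant shift per visit. Neither term lets one person drift, peak early or peak late relative to another. Neither makes readings 15 minutes apart more alike than readings 120 minutes apart. A sample that is half T1D and half T2D could well differ in both respects.

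In a crossover, a person's own curve shape is present on both days and should cancel when the bars are compared within that person. In this model it does not cancel; it enlarges the residual. Serial correlation has a separate effect: a single pooled standard error is too wide for contrasts close in time and too narrow for distant ones.

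Condition-by-time is the term that would show a spike. If its error rate depends on unknown nuisance correlation, a significant or non-significant result cannot be taken at face value. The stated hypothesis is that the sugar-free bar has no impact, so a test that is too conservative leans towards that conclusion.

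**Working it through.** **The plan's own figure.** For a within-between interaction with k = 2 groups, λ = f²·N·m/(1−ρ), df1 = (k−1)(m−1) and df2 = (N−k)(m−1), with no sphericity correction.
- m = 7, ρ = 0.7, N = 12: λ = 0.0625×12×7/0.3 = 17.5 on (6, 60) df, power 0.86.
- m = 14, ρ = 0.5, N = 12: λ = 0.0625×12×14/0.5 = 21 on (13, 130) df, power 0.84.
- m = 7, ρ = 0.5, N = 12: λ = 10.5, power 0.62; 18 would be needed.

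So 12 can be reproduced, but only by supplying a correlation the plan does not state and by assuming sphericity.

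**Inputs to the check.** From the documents: 20 participants, 2 conditions, the seven reading times, alpha 0.05. Assumed, because the documents give none: within-session SD σ = 1.0 mmol/L with correlation exp(−d/60) for readings d minutes apart; meter SD 0.4 (variance 0.16); a personal curve common to both days with SD τ = 0, 0.5 or 1.0 and the same correlation function; a 1.2 mmol/L peak difference for power (taken as triangular, peaking at 45 min). Time is categorical and data are complete.

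**Expected mean squares.** Among the 21 pairs of times, the gaps of 15, 30, 45, 60, 75, 90, 105 and 120 min occur 4, 5, 3, 3, 2, 2, 1 and 1 times, so the mean correlation is r = 0.476.
- Condition-by-time under the null, and participant×condition×time (114 df): σ²(1−r) + 0.16 = 0.524 + 0.16 = 0.684.
- Participant×time (114 df): 0.684 + 2τ²×0.524 = 0.684, 0.946, 1.732 for τ = 0, 0.5, 1.0.
- Participant×condition (19 df): σ²(1+6r) + 0.16 = 4.016.

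The correct error for condition-by-time is the first line. The planned model pools:
- Visit level absorbed by baseline (228 df): the average of the first two lines, 0.684, 0.815, 1.208. Numerator over denominator: 1.00, 0.84, 0.57.
- Participant intercept only (247 df): (114×0.684 + 114×participant×time + 19×4.016)/247 = 0.940, 1.061, 1.424. Ratio: 0.73, 0.64, 0.48.

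A ratio below 1 makes the test conservative. A ratio of 1.00 with serially correlated readings makes it liberal, because the nominal 6 numerator df are too many (estimated epsilon averages 0.59).

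**Simulated error rate and power (20×2×7).** The comparator is the F test on bar-minus-bar differences with Greenhouse-Geisser correction: false-positive rate 3.7–4.7%, power about 78%.

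| Personal-curve SD | Intercept only: false-positive / power | Visit level absorbed: false-positive / power |
|---|---|---|
| 0 | 2.2% / 72% | 7.0% / 87% |
| 0.5 | 1.4% / 64% | 3.9% / 81% |
| 1.0 | 0.3% / 40% | 0.8% / 54% |

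With the visit level absorbed and no personal curve, nominal 95% intervals for the bar difference in change from fasting cover 99% at 15 min and about 90% at 120 min. A T1D–T2D drift gap of 4 mmol/L over 2 h, with no other personal curve, gives 0.8% and 52% power against 77%; a gap of 2 mmol/L gives 3.9% and 81% against 78%.

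**Sensitivity.** Under other assumed shape SDs (up to 1.5) and serial correlations (0.6 to 0.9 per 15 min), the false-positive rate was 0.0–4.1% with an intercept only once any of these features was present, and 0.2% to about 9% with the visit level absorbed. When the model was exactly true it was 4.8%, so the defect comes from the missing terms and not from the sample size.

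**The case against.** The plan does not state that residuals are independent. It is silent, and an analyst could add a structure. That is fair, and it is why the point is conditional. But the random effects are named, and a model fitted as written has nothing else to carry curve shape or serial correlation.

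A reader might infer that the test is certainly not a 5% test, or that it loses a third of its power. The documents support neither, since they give no glucose SD, correlation, meter error or expected peak. At personal-curve SD 0.5 with the visit level absorbed, the two errors nearly cancel (3.9%) and no power is lost. A loss of about a third appears under that reading only when the personal-curve SD equals the session SD or the drift gap is 4 mmol/L.

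A reader might also infer that the test is liberal. That depends on reading "participant ID and baseline glucose values as random effects" as absorbing the visit level. With a participant intercept only, the test was conservative whenever these features were present.

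Finally, the paired t-tests on AUC and incremental AUC reduce each visit to one number and use within-person differences, so they are not exposed to this problem, and incremental AUC does capture a post-dose rise. This stands. It limits the claim that the analysis as a whole favours a no-impact result. It does not rescue the mixed model, because an AUC cannot show when the bars differ.

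**Conclusion.** The concern holds as a defect in the stated model, conditional on no residual structure being added. The direction and size of the error cannot be settled from the documents. Under the stated assumptions the false-positive rate lies between 0.3% and about 2% (intercept only) or between 0.8% and about 7% (visit level absorbed). Power lies between 40% and 72%, or between 54% and 87%, against about 78%; the 87% is bought with the inflated error rate. A nominal 5% test whose true level depends on unstated correlation and on an ambiguous baseline term should be corrected before analysis, even in a pilot. The AUC comparisons need no change on this account.

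**What to change.** State that time is categorical. Test condition-by-time on each participant's bar-minus-bar difference at each time, with a Greenhouse-Geisser or Huynh-Feldt correction. This removes the personal curve, is unaffected by visit level, and so does not depend on how baseline enters as a random effect.

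An alternative, which is a different model and was not simulated here, is to fit participant-by-time and participant-by-visit random effects, a spatial-power correlation within visit (suited to the unequal spacing), a separate measurement-error term, and Kenward-Roger degrees of freedom. Avoid a fully unstructured 7×7 covariance: it has 7×8/2 = 28 parameters for 20 participants.

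The cost is a few lines of analysis wording, slightly more work and no new data. The difference-based test needs complete pairs of curves, so the plan should say what happens if a reading is missing. If participants truly share one curve shape and the visit level is absorbed, apparent power falls from about 87% to 78%, but the 87% comes with a 7% false-positive rate.

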A glucose monitoring device (OneTouch Verio IQ® kit Blood glucose monitoring system) will be used to measure blood glucose levels before and after consumption of chocolates. Following consumption, measurements will be taken 15 min after, 30 min after, 45 min after, 60 min after, 90 min after, and 120 min after. Values will be registered on a form, stored on the meter and sent to research team by email. All to be done at home with no displacement.

Taste Test Questionnaire

Questionnaire is included as attachments and will be sent as link from the RedCap platform.

Protection of Human Subjects

All participants will be given a unique study code, with all data and information gathered connected with this code. Only the PI will have access to the master list linking the codes with participant names. Participant information and data will be either stored in a locked filing cabinet, or on an internal UBC network drive accessed only through a dedicated LAN internet connection on a password protected computer in the PIs laboratory with Salto passcard access only to the members of the research lab.

REDCap will be used as project management, storage of information, sending questionnaires and processing results. The REDCap platform is a secure web application for building and managing research data collection instruments. The platform is specifically designed to support online or offline data capture for research studies. The REDCap platform runs on server infrastructure physically located in BC, Canada, at the UBC University Data Centre (UDC).

POTENTIAL PROBLEMS AND ALTERNATIVE STRATEGIES

Diet compliance: Since the study involves a minor modification to diet, we do not anticipate that any adverse events due to the interventions will be seen.

Blood sampling:

When compared to traditional wet blood and plasma collection using venipuncture, capillary blood sampling is safer and easier, so much so that nearly anyone can perform the procedure, mainly diabetes patients who are used to doing finger pricks for glucose levels. However, risks associated with the process of finger-stick blood draws are minimized by usage of sterile and disposable material as well as hygiene procedures. Participants will receive their own kit with sterile material and instructions on procedure.

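### Two-period crossover analysed without a period term, and with no assured balance of bar order; adjusting for period with blocked order costs about 0.2 power points at N=20

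*Combined protocol and SAP*

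**What the plan says.** Research Method sets the design: "A double-blinded crossover pilot trial is proposed". The Day 1 and Day 2 schedule gives one bar per day, 2 to 7 days apart, with seven glucose readings each day. The allocation of order is described as "an equal chance of getting bar A or bar B first (similar to drawing a name out of a hat or flipping a coin". No block, stratum or fixed 10:10 split is stated.

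Statistical Analysis specifies a "linear mixed effects model including time, condition, and their interaction as fixed effects", with participant and baseline glucose as random effects. For the summary measures it says "Area under the curve and incremental AUC will be calculated and analyzed by paired t-test". No period or sequence term appears in either analysis.

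The Sample size section gives a requirement of 12 and a target of 20, the larger number partly to "enable potential sub-analyses of type 1 vs. type 2 diabetes". The target comprises 10 people of each type.

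**The concern.** In a two-period crossover, a paired difference contains the bar effect plus or minus any Day 1 to Day 2 shift, with the sign set by the order. An analysis that ignores order treats the shift as noise, which widens the interval even when orders are balanced. If orders are unbalanced, the shift no longer cancels and part of it enters the bar estimate.

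The lost precision matters because the stated hypothesis is that the sugar-free bar will not affect glucose. A wider interval makes a non-significant result more likely, and that result could be read as support. The possible type 1 and type 2 sub-analyses are more exposed, since groups of 10 become unbalanced easily.

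**Working it through.** **Inputs from the documents.** N=20 (10 per type), two periods, seven time points (0, 15, 30, 45, 60, 90, 120 min), alpha 0.05.

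**Assumptions.** Two-sided test. Paired differences have SD 1. The Day 2 minus Day 1 shift π is 0, 0.25 or 0.5 SD. The true bar effect is d=0.66 SD, chosen because it gives the paired test 80% power at N=20. The documents give no SD, within-person correlation or period effect.

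**The plan's own figure.** The requirement of 12 is for a within-between interaction with f=0.25 and 80% power. It reproduces with two groups, 14 measurements and a correlation of 0.5 (power 83.8%), none of which the plan states. It is not a calculation for the paired AUC comparison, so it cannot be used to cost the change.

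**Cost of adjusting when there is no shift** (noncentral t)
- Paired: noncentrality 0.66 x √20 = 2.952, 19 df, power 79.9%.
- Period-adjusted: SE = ½√(1/n₁ + 1/n₂). At 10:10 this is 0.2236, so the noncentrality is again 2.952, with 18 df and power 79.7%.
- At 8:12, SE = 0.2282 and power is 78.1%. At 6:14, SE = 0.2440 and power is 72.5%.
- Averaged over independent coin flips, adjusted power is 77.5%.

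**Effect of a shift on the paired test**
- Bias = π x (n₁ − n₂)/20. At 6:14 with π=0.5 this is 0.5 x 8/20 = 0.20 SD.
- At 10:10 the expected variance estimate is 1 + (20/19)π². The ratio of confidence interval widths, paired to adjusted, is √(1 + (20/19)π²) x t₁₉/t₁₈, which is 1.03 at π=0.25 and 1.12 at π=0.5.

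Simulated paired-test results (at least 200,000 runs per fixed split):

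| Split | π | Type I error | Power (by direction of shift) | Adjusted power |
|---|---|---|---|---|
| 10:10 | 0.25 | 4.3% | 78% | 80% |
| 10:10 | 0.5 | 2.9% | 72% | 80% |
| 8:12 | 0.5 | 4.5% | 57% or 85% | 78% |
| 7:13 | 0.5 | 6.5% | 49% or 89% | 76% |
| 6:14 | 0.25 | 6.4% | 64% or 89% | 73% |
| 6:14 | 0.5 | 9.8% | 42% or 93% | 73% |

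The adjusted test holds about 5% error throughout. Averaged over coin-flip splits, the paired test keeps 5.0% error at every π, with power 80.0%, 77.6% and 70.6% for π = 0, 0.25 and 0.5.

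**How likely imbalance is, if order is by independent coin flips** (binomial, n=20, p=0.5)
- Exactly 10:10: 17.6%.
- 8:12 or better: 73.7%.
- 7:13 or worse: 26.3%.
- 6:14 or worse: 11.5%.
- Within one type of 10, 3:7 or worse: 34.4%. In at least one of the two types: 1 − (1 − 0.344)² = 57%.

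**Mixed model.** This is a least-squares fit of the fixed effects at a 6:14 split with a unit Day 2 shift.
- Shift in the whole day's level: the condition effect moves by 0.4 and time x condition by 0.
- Shift in post-dose values only: time x condition moves by 0.4 at all six later times. Adding period alone leaves it at 0.4. Adding period and period x time takes it to 0.

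**AUC and iAUC.** By the trapezoid rule, a constant unit shift moves total AUC by 120 and net incremental AUC by 120 − 120 = 0. A post-dose shift moves both by 7.5 + 105 = 112.5. Subtracting baseline therefore protects only against the first kind of shift.

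**The case against.** The strongest reply is that randomising order already makes the paired t-test valid: averaged over coin flips its error is 5% whatever the shift. That is correct. The remaining issue is lost power, and bias conditional on the one split that is actually realised.

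Second, the harm depends on a shift that the documents do not report, and some text suggests it is small. Both tests take place at the same time of day after an overnight fast, and the Blood sampling section describes "mainly diabetes patients who are used to doing finger pricks for glucose levels". This also stands. At 0.25 SD the loss at 10:10 is only about 2 points. Near balance the paired test is conservative, and error exceeds 5% at 0.5 SD only for 7:13 or worse.

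Third, the 80% baseline is a calibration. If the effect were the one giving the paired test 80% power at N=12 (d=0.89), paired power at N=20 and 10:10 would be 96.5%, 95.9% and 93.9% for the three shifts, so the loss would be smaller.

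Fourth, the mixed-model figures omit the random effect for baseline glucose, whose coding is unclear and which might absorb part of a whole-day shift.

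Fifth, the coin-and-hat wording is a lay analogy, and drawing from a hat without replacement could balance the orders. The text does not commit to that.

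These points limit the size and weight of the concern. None of them identifies a place where the plan accounts for period.

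**Conclusion.** The concern holds as a worthwhile improvement, not as a demonstrated error. Neither planned analysis uses the period structure, and balance of order is not assured. With no Day 1 to Day 2 shift nothing is lost. With an assumed 0.5 SD shift, the paired test at 10:10 has 72% power instead of 80%, and at 6:14 it carries a bias of 0.20 SD with 9.8% error. A 6:14 or worse split has about a 12% chance if order is truly by independent coin flips.

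Confidence is medium, because the size of the shift, the effect of 0.66 SD and the coin-flip mechanism are all assumptions.

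**What to change.** Make these changes together, before allocation begins:

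- **Allocation.** Assign order from a prepared list in permuted blocks within type 1 and within type 2, giving 5 A-first and 5 B-first in each, with A and B denoting the same product in every kit.
- **AUC and iAUC.** Replace the paired t-test with the two-period crossover t-test, in which the bar effect is the mean of the two order-specific mean differences.
- **Mixed model.** Add both period and period x time as fixed effects. Period alone does not protect time x condition.
- **Sub-analysis, if done.** Pre-specify it as condition x type and condition x type x time. No type main effect is needed for the bar comparison, because type cancels within person.

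**Cost.** The changes need a prepared list, one degree of freedom in the t-test and, with time categorical, 1 + 6 = 7 parameters in the mixed model; the power cost of those parameters was not computed. For the t-test at N=20 and 10:10, power goes from 79.9% to 79.7%. The cost is larger elsewhere: about 0.8 points at N=12 and 1.3 points in a subgroup of 10 (each at its own 80% effect), and about 1.9 points if dropout leaves 8:12.

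The parts depend on each other. At a 0.5 SD shift, blocking alone gives 72% power, the period term alone 77.5%, and both 79.7%. With no shift, a period term without blocking loses about 2.5 points. Period adjustment does not remove carryover.

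### The paired t-test on total AUC leaves the day-specific fasting reading unused as a covariate; this can cost precision, not validity, and the loss cannot be sized from the documents

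*Combined protocol and SAP*

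**What the plan says.** The Statistical Analysis section plans two things. The glucose time course goes into a mixed model with time, condition and their interaction as fixed effects and "participant ID and baseline glucose values as random effects". Then: "Area under the curve and incremental AUC will be calculated and analyzed by paired t-test". No covariate is named for these tests, and incremental AUC (iAUC) is not defined as net area or positive area only.

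The day-specific fasting value exists. Under Study Timeline, both Day 1 and Day 2 begin with: "Measure glucose levels before chocolate consumption and write down value on Glucose levels form". Readings are taken at "before consumption, 15 min after, 30min after, 45min after, 60min after, 90min after, 120min after". The two mornings are not interchangeable: "Eligible participants will complete 2 experimental trials separated by approximately 2-7 days", each carried out at home "in the morning after an overnight fast, refraining from diabetic medications".

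**The concern.** Total AUC over 120 minutes contains that morning's fasting level, carried forward to whatever extent it persists. The paired difference cancels what is stable in a person between the two days. It does not cancel a fasting value that happens to be higher on one morning. That variation enters the standard error of the AUC comparison, although a measured covariate could explain part of it.

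iAUC handles this only by subtraction, with a slope of exactly 1. A single finger-stick reading, with its meter error, is then spread across 120 minutes. If fasting differences carry through only in part, subtraction over-corrects.

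Precision matters here because the stated hypothesis is that the test bar will not affect glucose. An imprecise, non-significant AUC test could be read as support for it. Two unranked tests that treat baseline differently may also disagree for reasons unrelated to the bars.

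**Working it through.** **The plan's own figure.** The Sample size section gives 12 participants for a within-between interaction (f = 0.25, alpha 0.05, power 80%). With 2 groups, 14 readings per person (2 days × 7), correlation 0.5 and sphericity, all assumed, the noncentrality is 0.25² × 12 × 14 / (1 − 0.5) = 21.0 on 13 and 130 df. Power is 83.8%, against 73.5% for 10 participants, so 12 can be reproduced. With 7 readings the same formula gives 18 at correlation 0.5. Either way the figure concerns an interaction and does not establish power for the paired t-tests.

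**Total AUC.** From the documents: 20 planned participants, alpha 0.05 (two-sided assumed). Assumed: a bar effect of 0.5 SD of the paired AUC difference, 10 participants per order, and r, the correlation between the paired fasting difference and the paired AUC difference.

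- Unadjusted: standardised effect 0.5, 19 df, power 56%.
- Adjusted for fasting difference and period: residual variance is multiplied by (1 − r²). Estimating the slope multiplies the variance of the bar effect by about 1 + 1/16. 17 df remain.

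| Assumed r | (1 − r²)(1 + 1/16) | Standardised effect | Power by formula | Power by simulation (40,000 runs) |
|---|---|---|---|---|
| 0 | 1.063 | 0.485 | 53.4% | 54.0% |
| 0.3 | 0.967 | 0.508 | 57.3% | 57.6% |
| 0.5 | 0.797 | 0.560 | 65.6% | 65.7% |
| 0.7 | 0.542 | 0.679 | 81.7% | 81.9% |
| 0.8 | 0.382 | 0.808 | 92.6% | 92.6% |

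Break-even on variance: (1 − r²)(1 + 1/16) = 1 gives |r| = √(1/17) = 0.24.

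**iAUC.** Let k be the SD of 120 × fasting difference divided by the SD of the AUC difference (also assumed). The variance of the net iAUC difference is 1 + k² − 2rk = (1 − r²) + (k − r)². The true slope of AUC on 120 × fasting is r/k, so the excess (k − r)² vanishes when that slope is 1.

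| r | k | Slope r/k | iAUC variance | iAUC power | Adjusted power |
|---|---|---|---|---|---|
| 0.3 | 1 | 0.3 | 1.40 | 43% | about 58% |
| 0.3 | 0.5 | 0.6 | 0.95 | 59% | about 58% |
| 0.5 | 1 | 0.5 | 1.00 | 56% | 66% |
| 0.5 | 0.5 | 1.0 | 0.75 | 69% | 66% |
| 0.7 | 1 | 0.7 | 0.60 | 78% | 82% |
| 0.7 | 0.7 | 1.0 | 0.51 | 84% | 82% |

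**Simulation with trapezoid AUC.** Twenty participants; assumed day-to-day fasting SD 0.5–1.5 mmol/L, carry-through 0.5–1.0, response SD 1.0, meter SD 0.4 and peak effect 1.0 mmol/L. This gives nine scenarios, with the fasting difference as the only covariate. Power was 25–79% for the AUC t-test, 51–75% for net iAUC and 73–80% adjusted. Against adjustment, AUC lost 1 to 47 points in all nine. iAUC lost 1 to 28 points in seven and was about 2 points better in two, where fasting differences carried through fully. Type I error was about 5% for every method.

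**The case against.** A paired t-test under randomised order is valid. One might infer that a chance fasting imbalance could pass for a bar effect and that the AUC result is therefore biased. The documents do not support that: order is randomised, and day-to-day fasting variation is already in the test's standard error. With an assumed fasting SD of 1 mmol/L, chance moves the mean AUC difference by 120 × √2 × 1 / √20 = 37.9 mmol/L·min (one standard error). This sounds large, but the documents give no AUC effect or total SD to set it against. This objection stands in full.

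A reader might also infer that the plan ignores baseline. It does not: iAUC uses each day's fasting value, and the mixed model includes baseline, though as a random effect. Neither adjusts the total AUC test. The AUC tests are not named as primary, and the study describes itself as a pilot.

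A third tempting reading is that iAUC is clearly inferior, for example 43% power against about 58% at r = 0.3. That rests on k = 1. At k = 0.5 iAUC has 59% and matches the adjusted model. The documents give neither r nor k.

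Finally, adjustment is not free. If the correlation is near zero it loses 2 to 3 points of power.

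**Conclusion.** The point holds as a matter of precision and is firmest for total AUC. The plan collects a day-specific fasting value and leaves it out of that test, so within-person fasting differences remain as noise. The gain from using it ranges from slightly negative (about 54% against 56% at r = 0) to large (92–93% at r = 0.8), under an assumed effect of 0.5 SD. Over iAUC the gain is greatest when the true slope is well below 1 and fasting differences make up much of the AUC noise; it is nil or slightly negative when the slope is near 1. The direction follows from the design. The size rests on correlations and SDs that the documents do not give. This is a cheap improvement to the plan, not the correction of an invalid test.

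**What to change.** Replace the two paired t-tests with one prespecified model, in either form:

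- Regress each person's between-bar AUC difference on the between-day fasting difference (taken in the same bar direction), plus order coded +0.5 and −0.5. The intercept is then the bar effect at zero fasting difference. With 0/1 coding it would be the effect in one order, mixed with the period effect.
- Equivalently, model AUC with condition, period, participant (as a fixed effect) and the day-specific fasting value as a fixed covariate.

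Define iAUC as net area. Net iAUC is AUC minus 120 × fasting, so with the fasting difference in the model only the slope changes, by 120. The bar effect and p-value are identical for AUC and net iAUC, and one test serves for both. This is not so for positive-area-only iAUC.

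The cost is a sentence or two of analysis text and two degrees of freedom, with the small loss of power noted above if fasting and AUC differences are nearly uncorrelated. No further data, visits or participants are needed.
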